- a) Worsening markers of inflammation and heart disease across the spectrum stratified by presence and absence of excess VAT and presence and absence of coronary plaque (i.e. increased worsening across the following groups: low VAT/absence of plaque, low VAT/presence of plaque, high VAT/absence of plaque, high VAT/presence of plaque).

III. Subject Selection

Inclusion/Exclusion:

Inclusion Criteria: Up to 160 HIV male and female subjects will be consented to achieve the number of evaluable subjects. 42 subjects will be consented for the optional study.

Subjects will be included for:

- 1) Ages 40-65 years
- 2) Antiretroviral use (ART) >12 months and viral load <100 copies/mL
- 3) VAT > 110cm²

Exclusion Criteria:

- 1) Antihypertensive use including, ACE Inhibitor, ARB, MR blockade, diuretic, potassium (K) supplementation; or BP > 140/90 mmHg. Stable use (>3 months) of beta-blockers or calcium channel blockers (CCB) (except verapamil) is allowed.
- 2) Unstable statin use <12 months. Stable use (>12 months) is allowed.
- 3) Use of full dose ritonavir, nelfinavir, clarithromycin, and other strong inhibitors of CYP3A4, as well as CYP3A4 inducers.
- 4) Continuous oral steroid use (equivalent to prednisone \geq 5 mg daily) within the last 3 months.

**MIneralocorticoid Receptor Antagonism for CardiovascuLar hEalth in HIV
The MIRACLE HIV Study**

- 5) Uncontrolled diabetes requiring insulin and/or HbA1c > 7.5%.
- 6) Creatinine (Cr) > 1.5 mg/dL or estimated GFR<60 mL/min/1.73m².
- 7) K > 5.5 mEq/L.
- 8) Hemoglobin < 10 g/dL.
- 9) Known liver disease or ALT >3x ULN.
- 10) History of congestive heart failure, stroke, myocardial infarction, or known coronary artery disease.
- 11) Pregnant, actively seeking pregnancy or breastfeeding. Women of childbearing age may be on a non-hormonal form of contraception.
- 12) Estrogen, progestin derivative, or other sex steroid use within last 3 months. Stable physiologic testosterone replacement (> 3 months) is acceptable.
- 13) Current bacterial or other infections.
- 14) Active substance abuse.
- 15) Significant radiation exposure over the course of the year prior to randomization (e.g., radiation therapy, PCI, catheter ablation of arrhythmia) within 12 months of randomization.
- 16) Previous reaction or contraindication to gadolinium.
- 17) Coronary artery luminal narrowing >70% on coronary CTA.

Source of subjects and recruitment methods:

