Aim VI: In an exploratory analysis, subjects will be enrolled using a factorial sampling strategy into 4 analytic strata (low VAT/absence of plaque, low VAT/presence of plaque, high VAT/absence of plaque, high VAT/presence of plaque). Using this design, we will first analyze whether there are differences in markers of inflammation and heart disease by VAT status (main effects model comparing presence and absence of excess VAT) using student's t-test for variables that are normally distributed or Wilcoxon rank sum test for variables that are not normally distributed. Based on the exclusion criteria excess VAT is determined to be $>110\text{cm}^2$. After assessing for differences in VAT in the main effects model, we will examine the degree to which markers of inflammation and heart disease are related to coronary plaque in both the high and low VAT groups, and whether this relationship is stronger in the coronary plaque group as a result of increased VAT using ANOVA for variable that are normally distributed and Kruskal-Wallis Test for variables that are not normally distributed.

VII. Risks and Discomforts

Blood Drawing: The total blood drawn for subjects completing the study is equivalent to approximately 560 ml (over a period of 12 months). This quantity of blood drawing does not pose excessive risk to subjects. By comparison, the Red Cross allows a healthy adult to donate 1 pint of blood every 8 weeks, which is about 473 ml. Subjects with a hemoglobin < 10 mg/dL will be excluded from the study. There will be minimal risk and

Mineralocorticoid Receptor Antagonism for Cardiovascular Health in HIV The MIRACLE HIV Study

discomfort associated with blood drawing and IV placement. The risks of these procedures are minor bruising or bleeding at the site of the blood draw or IV catheter or feeling faint. Standard clean insertion techniques will be utilized to minimize risk of infection.

Intravenous Catheter Placement: There are minor risks and discomforts associated with having an intravenous line and with injection of contrast agent through the intravenous line, including the possibility of bleeding, pain, inflammation (redness and swelling), and leaking of contrast agent outside of the vein at the site of the IV. These problems usually self-resolve or only require minor treatments, such as application of an ice-pack or slight pressure for a few minutes.

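### Aim VI (exploratory): no named test uses the hypothesised order of the four strata, Kruskal-Wallis cannot test whether the plaque relation is stronger with high VAT, and the ANOVA model is not specified

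*Combined protocol and SAP*

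**What the plan says.** Section II, Specific Aim VI, hypothesis a) predicts "Worsening markers of inflammation and heart disease across the spectrum stratified by presence and absence of excess VAT" and of coronary plaque. It fixes the sequence: "increased worsening across the following groups: low VAT/absence of plaque, low VAT/presence of plaque, high VAT/absence of plaque, high VAT/presence of plaque".

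Section VI, Aim VI, gives the analysis:

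- Status and design: "In an exploratory analysis, subjects will be enrolled using a factorial sampling strategy into 4 analytic strata".
- Step 1 is a "main effects model comparing presence and absence of excess VAT", done with a t-test or Wilcoxon rank sum test.
- Step 2 first looks at plaque within each VAT level: "we will examine the degree to which markers of inflammation and heart disease are related to coronary plaque in both the high and low VAT". It then asks "whether this relationship is stronger in the coronary plaque group as a result of increased VAT using ANOVA" for normal variables, or "Kruskal-Wallis Test for variables that are not normally distributed".

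The text does not say whether the ANOVA is one-way or two-way. It names no interaction term, trend test or ordered contrast, and gives no rule for interpreting a significant result. It also gives no sample size, SD, effect or power for Aim VI. Section III says "42 subjects will be consented for the optional study", but 42 is also the size used for the Aim IV and V substudy, so it cannot safely be taken as the Aim VI number.

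**The concern.** There are two questions, and the named tests do not match them.

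1. **Order.** The only hypothesis stated for Aim VI is a directional ordering of four groups. Neither an omnibus ANOVA nor Kruskal-Wallis uses the order of the groups.
2. **Effect modification.** Whether the marker-plaque relation is stronger with high VAT compares two differences. Kruskal-Wallis tests only whether the groups differ somewhere. ANOVA answers the question only if a VAT x plaque term is fitted and read.

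At stake is what an Aim VI report could claim. A small omnibus p-value would be compatible with additive effects, with VAT acting alone, or with the reverse of the hypothesised order.

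**Working it through.** The plan states no figure for Aim VI, so there is none to reproduce. The check asks how often each test rejects when the claim it would be used for is false.

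**Assumptions (not in the documents).** Normal data, SD 1, equal strata, n = 20 per stratum (range 10 to 40), two-sided alpha 0.05. Trend rejections are counted only in the hypothesised direction (one-sided 0.025). Means are in SD units, in the order low VAT/no plaque, low VAT/plaque, high VAT/no plaque, high VAT/plaque.

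**Formulas.**

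- Four-group F test: noncentrality λ = n Σ(μᵢ − μ̄)², with 3 and 4n − 4 df.
- Interaction: [(μ₄ − μ₃) − (μ₂ − μ₁)] / (2/√n).
- Linear trend: δ = Σwᵢμᵢ / √(Σwᵢ²/n), with w = (−3, −1, 1, 3). Since Σwᵢ² = 20, δ = Σwᵢμᵢ at n = 20.
- Kruskal-Wallis: simulation, 4,000 runs per scenario.

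**Results at n = 20 per stratum.**

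| True means | λ | F | Kruskal-Wallis | Interaction | Trend |
|---|---|---|---|---|---|
| Additive: 0, 0.6, 0.6, 1.2 | 14.4 | 89% | 86% | 5% | 94% |
| VAT only: 0, 0, 0.8, 0.8 | 12.8 | 85% | 83% | 5% | 88% |
| Only low VAT/plaque raised: 0, 0.8, 0, 0 | 9.6 | 72% | 69% | 42% | 0.3% |
| Order reversed: 0.9, 0.6, 0.3, 0 | 9.0 | 69% | 64% | 5% | about 0% |
| Order as hypothesised: 0, 0.3, 0.6, 0.9 | 9.0 | 69% | 66% | 5% | 84% |

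**Interaction.** In the additive row the contrast is (1.2 − 0.6) − (0.6 − 0) = 0, so the plaque relation is not stronger with high VAT. The omnibus tests still reject in 86% to 89% of trials (50% to 55% at n = 10, over 99% at n = 40). In the third row the contrast is −0.8: the plaque relation is weaker with high VAT, yet both omnibus tests reject in about 70%. If the plan meant only high against low VAT within the plaque strata, that is one two-group contrast, and the omnibus test does not isolate that either.

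**Order.** The last two rows have the same λ, so F has identical power whether the hypothesis is true or exactly backwards. In one simulated data set, F = 2.480 and H = 7.408 under each of three orderings of the strata.

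**Power for the ordering.** Take means 0, 0.25, 0.5, 0.75.

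- F: λ = 20 × (2 × 0.375² + 2 × 0.125²) = 6.25, power 51%.
- Trend: δ = −0.25 + 0.5 + 2.25 = 2.5, power 69%.
- The planned VAT t-test: difference 0.625 − 0.125 = 0.5, within-group SD √(1 + 0.125²) = 1.008, δ = 0.5 / (1.008 × √(2/40)) = 2.22, power 59%.

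F against trend is 26% against 41% at n = 10, and 85% against 94% at n = 40.

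**What an interaction term could detect.** With 80% power the detectable difference of differences is (1.960 + 0.842) × 2/√n SD: 1.77 SD at n = 10, 1.25 SD at n = 20 and 0.89 SD at n = 40.

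**The case against.** The strongest reply is that the plan says ANOVA, not one-way ANOVA, and says it beside a factorial sampling strategy and a main effects step. A two-way ANOVA with a VAT x plaque term is a fair reading, and it would keep rejection at 5% under additivity. This stands. A reader might infer that the plan specifies a one-way test and so the wrong test. The text does not support that, because pairing a parametric test with a rank fallback is routine in this protocol. For normal markers the fault is under-specification. The reply does not rescue Kruskal-Wallis, and a two-way ANOVA still ignores the hypothesised order. Transformation before multivariable modelling appears under Aim I, but the Aim VI text sends non-normal markers to rank tests.

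Three further limits stand:

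- A reader might infer that Aim VI hypothesises an interaction. It does not: Section II states only ordered worsening, and the 'stronger' question appears in the analysis text.
- A reader might infer that the sponsor will misread an omnibus result. That would be a prediction, because no interpretation rule is written.
- The VAT comparison in step 1 is a focused test close to the hypothesised order. It recovers part of the power lost: 59%, between 51% and 69%.

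Nor does a significant trend prove every step. It rejects in 88% when VAT alone acts. With the middle strata swapped (0, 0.6, 0.3, 0.9; δ = 2.4) it rejects in 66%, against 69% for F.

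**Conclusion.** The concern holds in limited form. For non-normal markers, the named test cannot answer the plan's own question about effect modification. For normal markers, the plan does not say whether the ANOVA has the term that would answer it. On either reading, no named test uses the ordering that is the sole Aim VI hypothesis, so a significant omnibus result would be evidence for neither statement.

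The mismatch itself follows from the text and needs no assumption. Its size does: every percentage rests on assumed stratum sizes, SD and effects.

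Severity is minor. Aim VI is labelled exploratory and rests on an optional blood-sampling visit for people who did not qualify for the main study. It does not touch the randomised comparison.

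**What to change.** In Section VI, Aim VI:

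1. Specify a two-way linear model for each marker with VAT, plaque and VAT x plaque, on log- or otherwise transformed values if non-normal. Read the 'stronger' question from the interaction estimate and its confidence interval, on the stated scale.
2. Test the ordered hypothesis with a 1-df linear trend contrast, or Jonckheere-Terpstra if normality is not achieved, and state the direction that counts as support.
3. Report the four stratum estimates and the three adjacent differences with confidence intervals, because a significant trend alone does not establish each step.
4. State the number of subjects expected per stratum, so that readers can judge precision.

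The cost is a few sentences and no extra data. The downside is modest interaction power: if only high VAT/plaque is raised, by 0.8 SD, power is about 42% at an assumed 20 per stratum. A non-significant interaction should therefore not be reported as absence of effect modification.

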Baseline Visit 2 (RAAS Characterization): After Baseline Visit 1, subjects will be placed on an isocaloric low sodium diet for 6 days prepared by the metabolic phenotyping core at the BWH Center for Clinical Investigation for assessment of RAAS activation. Subjects will be asked only to consume the prescribed diet, containing 10 ± 2 mEq Na⁺, 100 ± 2 mEq K⁺, and 1000 ± 50 mg Ca²⁺ per 24 hours.

- 1) 24 hr urine will begin on the morning of this visit for volume, Na, K, Cr, cortisol, and aldosterone excretion rate.
- 2) Urine pregnancy test for females as appropriate.
- 3) Urine Na and Cr (rescheduled if subject is not in sodium balance).
- 4) Interval history and physical, including orthostatics.
- 5) Subjects will begin fast and lie supine overnight.
- 6) Fasting blood for PRA, serum aldosterone, K. DNA collection for genetic testing is optional.
- 7) Resume ad lib diet and administer study medication (eplerenone vs. placebo) to be started on the following day.

Substudy Visit 1 (Optional): Subjects will present on a low carbohydrate diet, after an overnight 12 hr fast. We will obtain:

- 1) STAT serum pregnancy test for females as appropriate.
- 2) Cardiac ¹⁸F-FDG-PET/CT to assess arterial inflammation.

Randomization and Blinding: Subjects will be randomized 1:1 to receive eplerenone

**Mineralocorticoid Receptor Antagonism for Cardiovascular Health in HIV
The MIRACLE HIV Study**

50mg daily or identical placebo for 12 months. The randomization list, stratified by gender, statin use and presence of plaque will be generated by the biostatistician and kept by the research pharmacy. Daily dosing starts at 50 mg daily for the first week to avoid hypotension and will be increased to 50 mg twice daily at the 1 week safety visit. The study will be double-blinded. All subjects will receive lifestyle modification as described below.

Safety Visits (1 wk, 2 wk, 4 wk, 3 mo, 6 mo, 9 mo post baseline visits): Subjects will only present after an overnight 12 hr fast for the 6 month visit. All safety visits include:

- 1) Urine pregnancy test for females.
- 2) Interval history and physical, including vitals.
- 3) Blood for Cr, K. Blood for markers of heart disease and inflammation for the 6 month visit only.
- 4) Collection of used study drug and provision of new supply.

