- 5) Standardized lifestyle counseling as per goals derived from the AACE and NCEP-ATP III guidelines and modeled after the Diabetes Prevention Program. At the 1 week visit, the study dose will be escalated to 50mg twice daily as tolerated based on blood pressure and labs.

12 Month Visit: Same as Baseline Visit 1

Substudy Visit 2 (Optional): Same as Substudy Visit 1

COVID19 Contingency Plan: MGH and BWH have instituted restricted visits for research purposes in response to the evolving COVID-19. These restrictions have prompted the following changes to the study:

1) We may conduct visits remotely until restrictions are lifted. Remote visits will be conducted over zoom video conferencing or telephone and every attempt will be made to keep the visit schedule the same. Changes may occur to the visit schedule due to factors related to covid19. During these visits, someone from the study staff will contact the subject (via zoom video conferencing or telephone) and may conduct the following research activities:

- Consenting*
- Obtaining information about past and present health
- Questionnaires
- Lifestyle Counseling
- Obtaining information related to safety assessments

2) We may ship study drug directly to the subject.

3) If blood work cannot be obtained at the study site, we may ask the subject to have labs performed locally. We will provide a lab requisition and help locate a facility.

4) We will try to arrange for assessments to occur remotely and continue to follow the visit schedule. Some study procedures require a visit to the study site, for example, imaging procedures. We may provide the subject with additional study drug until we are able to perform the study procedure, and this may extend the visit schedule. If a study procedure requires an in-person visit and cannot be scheduled at the study site due to

Mineralocorticoid Receptor Antagonism for Cardiovascular Health in HIV The MIRACLE HIV Study

COVID19 policies, then the procedure may be omitted.

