CTA contrast medium: CTA requires the intravenous administration of iodinated contrast medium. These contrast media have been known to cause renal failure, particularly in subjects with a pre-existing renal impairment. Adequate hydration will also be emphasized to each study participant. The contrast dose in coronary CTA has decreased with the introduction of faster scanners. The dose required will be between 60 to 100 ml. Allergic reactions to iodinated contrast media may cause skin reactions or in very rare occasions result in breathing difficulty and hypotension. Subjects will be closely

Mineralocorticoid Receptor Antagonism for Cardiovascular Health in HIV The MIRACLE HIV Study

monitored for the development of any allergic reactions. To minimize risk from iodinated contrast, subjects with previous allergic reactions to iodine-containing contrast media or signs of renal failure or history of renal disease will be excluded from the CTA study. Additional safety criteria will be implemented by measuring serum creatinine and excluding subjects with serum creatinine >1.5 mg/ml or estimated GFR <60 mL/min/1.73m 2 . Metformin use is an exclusion criteria for the study, so the risk of lactic acidosis will be avoided.

Nitroglycerin: Nitroglycerin is commonly used in subjects with angina pectoris and is generally considered safe. The side effects and risks of nitroglycerin are generally mild and of short duration and include hypotension, tachyarrhythmia, headache, lightheadedness, and visual disturbance. Subjects who are on sildenafil, tadalafil, or vardenafil (PDE5 inhibitor) will need to stop these drugs at least 5 days prior to receiving nitroglycerin on the day of the coronary CTA scan. If baseline systolic blood pressure is below 90, nitroglycerin will not be given. If a participant's blood pressure were to drop precipitously or if the participant develops symptoms, standard clinical care will be provided. Other contraindications to nitroglycerin include severe aortic stenosis or hypertrophic obstructive cardiomyopathy.

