Eplerenone: The eplerenone dose of 50mg daily has been used safely in previous studies to improve coronary circulation in individuals with Type 2 diabetes and by others in numerous studies of patients with CVD. This dose is FDA approved for indefinite use in patients with hypertension or left-ventricular dysfunction following myocardial infarction. Hyperkalemia is a potential side effect of eplerenone use, and any subject with serum K > 5.5 mEq/L at screen will be excluded. During the study, a subject who has an elevated K of > 5.5 mEq/L at any study visit will have a recheck; if the K remains elevated after recheck, the dose will be decreased to 50mg daily. If the K remains elevated > 5.5 mEq/L, the subject will be excluded from the study. Additionally, subjects who experience symptoms of hyperkalemia and have a K > 5.0 mEq/L will be excluded from continued participation in the study. Subjects who have hypotension (SBP<90 mmHg) at any study visit after titration to full dose eplerenone 50mg twice daily will be given a dose reduction to 50 mg daily. If a subject remains hypotensive (SBP <90 mmHg) or symptomatic of hypotension at the reduced dose they will be dropped from the study. Since subjects with renal insufficiency may require reduced dosing based on creatinine clearance, subjects with serum creatinine > 1.5 mg/dl will also be excluded. Other rare side effects include dizziness, fatigue, and diarrhea; these will be assessed for throughout the study. The effect of eplerenone on an embryo, fetus, or on a breastfeeding infant, is unknown and may be harmful. Because of these unknown risks, women cannot take part in this study if they are: pregnant, trying to become pregnant, breastfeeding. If women become pregnant or think they are pregnant during the study, they must stop taking the study medication and will be withdrawn from the study. We have received FDA IND exemption for the use of eplerenone in HIV for insulin resistance and recently received an FDA IND exemption for application in CVD indices in HIV. Protease inhibitors with the most significant effect on CYP3A4 will be exclusionary as in our prior trials of HIV patients. We will also exclude subjects using other strong inhibitors of CYP3A4, as well as CYP3A4 inducers. Furthermore, all subjects will be carefully monitored for side effects, including frequent potassium and BP monitoring. A 50mg twice daily dose of eplerenone has been chosen, such that even if concentrations do increase somewhat through pharmacokinetic interactions, we expect the drug to be well tolerated. The dose of 100 mg/day has been effective in numerous studies of non-HIV patients and is expected to be effective in the proposed studies.

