Hyperkalemia is a potential side effect of eplerenone use, and contraindications for the use of eplerenone include serum K > 5.5 mEq/L at initiation. Therefore, any subject with serum K > 5.5 mEq/L at screen will be excluded from the study. During the study, a subject who has an elevated K of > 5.5 mEq/L at any study visit will have a recheck; if the K remains elevated after recheck they will be excluded from the study. Additionally, subjects who experience symptoms of hyperkalemia and have a K > 5.0 mEq/L will be excluded from continued participation. Subjects who have symptomatic hypotension at any study visit after titration to full dose eplerenone 50mg twice daily will be given a dose reduction to 50 mg daily. Since patients with renal insufficiency may require reduced dosing based on creatinine clearance, subjects with renal insufficiency (serum creatinine > 1.5 mg/dl) will also be excluded from participation. Other side effects have been reported and include dizziness, fatigue, diarrhea, headache, stomach pain, cough, breast enlargement or breast enlargement, rash, abnormal vaginal bleeding. Rare but serious side effects include chest pain, tingling in arms and legs, loss of muscle tone, weakness or heaviness in legs, confusion, lack of energy, cold, gray skin or irregular heartbeat. These potential side effects will be assessed for throughout the study. Exclusion criteria during the study include initiation of ACE-I, ARB, or spironolactone; Hgb < 10; ALT > 3.0x ULN; persistent hyperkalemia (K > 5.5 mEq/L despite recheck and/or symptoms of hyperkalemia if K > 5.0 mEq/L). If a subject remains hypotensive (SBP < 90 mmHg) or symptomatic of hypotension after a dose reduction of eplerenone to 50 mg for this same reason during the study, they will be dropped from the study.

Data Safety Monitoring Plan

Prior to the start of study, a data safety monitoring board will be created and this board will consist of a statistician, a clinician not directly related to the research project, but one who is familiar with HIV infection and its complications, and a member of the HIV community. This board will meet quarterly to review any potential side effects or adverse events in relation to the use of eplerenone or participation in the study. The

Mineralocorticoid Receptor Antagonism for Cardiovascular Health in HIV The MIRACLE HIV Study

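### The two on-study potassium rules give different actions for a confirmed K above 5.5 mEq/L, and the metformin exclusion is missing from the lists that staff apply

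*Combined protocol and SAP*

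**What the plan says.** **Potassium.** Section VII, Eplerenone, requires a recheck when K exceeds 5.5 mEq/L at a study visit. If the recheck is still high, "if the K remains elevated after recheck, the dose will be decreased to 50mg daily". Removal is a later step: "If the K remains elevated > 5.5 mEq/L, the subject will be excluded from the study". Section IX starts from the same trigger and the same recheck, but then says "if the K remains elevated after recheck they will be excluded from the study". Its list of on-study exclusions repeats this as "persistent hyperkalemia (K > 5.5 mEq/L despite recheck and/or symptoms of hyperkalemia if K > 5.0 mEq/L", with no mention of an earlier dose reduction.

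**Dose and visits.** Section V starts everyone on 50 mg daily and then titrates: "At the 1 week visit, the study dose will be escalated to 50mg twice daily as tolerated based on blood pressure and labs". The schedule reads "Safety Visits (1 wk, 2 wk, 4 wk, 3 mo, 6 mo, 9 mo post baseline visits", with K drawn at each. K is also drawn at the Bionutrition Visit before month 12 and at the 12 Month Visit, which repeats Baseline Visit 1.

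**Metformin.** Section VII, CTA contrast medium, states: "Metformin use is an exclusion criteria for the study, so the risk of lactic acidosis will be avoided". The only diabetes criterion in Section III is number 5: "Uncontrolled diabetes requiring insulin and/or HbA1c > 7.5" percent.

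**The concern.** Hyperkalemia is the first side effect of eplerenone named in both sections, so its stopping rule should read the same wherever staff look. As written, the same laboratory result leads to continued study drug at 50 mg daily or to removal from the trial, depending on which section is open. That affects the subject's safety management and also whether the subject continues towards month 12.

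The metformin sentence is a risk statement: it tells the reader that a hazard of iodinated contrast has been dealt with by eligibility. Section IV makes eligibility depend on meeting all the enrollment criteria, and someone screening from that list has no prompt to ask about metformin. The first coronary CTA takes place at Screening Visit 2 and the second before month 12.

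**Working it through.** No formula applies to the main question. The check is a comparison of the texts.

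**1. The potassium rules side by side, for a subject on 50 mg twice daily**

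| Step | Section VII, Eplerenone | Section IX |
|---|---|---|
| K >5.5 at a visit | Recheck | Recheck |
| Recheck still high | Reduce to 50 mg daily, stay in study | Exclude |
| K still >5.5 after reduction | Exclude | Not reached |
| Symptoms with K >5.0 | Exclude | Exclude |

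The rules part company in the second row only. Section IX does not look like shorthand for Section VII: it states immediate exclusion twice, and in the same paragraph it writes out a dose reduction for hypotension.

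**2. When the conflict can arise**

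- Safety visits: 6, less the week-1 visit (the subject is still on 50 mg daily) = 5 (2 wk, 4 wk, 3, 6 and 9 mo).
- Plus the Bionutrition Visit before month 12 and the 12 Month Visit: 5 + 2 = 7 scheduled checks.

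At the 12 Month Visit the treatment period is ending, so the choice matters least there.

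**3. A gap inside the Section VII rule**

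A subject already on 50 mg daily (at week 1, never escalated, or reduced for hypotension) cannot be reduced to 50 mg daily. Section VII does not say what to do at a confirmed K >5.5 in that case.

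**4. Where metformin is named**

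| Place | Metformin named? |
|---|---|
| Section III, 17 exclusion criteria | No |
| Section IX, on-study exclusion list | No |
| Section V, reasons for not doing the CTA (contrast reaction or contraindication) | No |
| Appendix A, CYP3A4 inhibitors | No |
| Section VII, CTA contrast medium | Yes, the only mention |

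Criterion 5 removes insulin-requiring diabetes and HbA1c above 7.5%. A metformin user without insulin and with HbA1c at or below 7.5% therefore passes every listed criterion on diabetes.

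**5. Contrast exposure at stake**

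Section VII gives 60 to 100 ml per CTA. Section V adds a test bolus of about 20 ml, so 60 + 20 = 80 ml to 100 + 20 = 120 ml per scan, and 160 to 240 ml over two scans. This describes the exposure only. The documents do not give the size of the lactic acidosis risk.

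**The case against.** **On potassium.** The gap is a single step. Both rules require a recheck, both end the 100 mg/day dose, both remove a subject whose K stays above 5.5, and both remove symptomatic subjects above 5.0. This stands, and it limits the severity. A reader might infer that a subject with confirmed hyperkalemia could be left on full dose; neither section allows that. The conflict itself remains, because continuing drug at half dose and leaving the study cannot both be done.

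**On metformin.** Section VII is protocol text and states the exclusion plainly. The protocol places other limits outside Section III, such as the 15 mSv prior-radiation ceiling and the 50% left main threshold. The Section IX list is worded as inclusive and also omits pregnancy, which Section VII makes a reason for withdrawal. Creatinine and eGFR limits give separate protection, and creatinine is drawn at the Bionutrition Visit where the second CTA is scheduled. All of this is fair. A reader might infer that no metformin rule exists, or that metformin users are being scanned; the documents show neither. They show a rule stated once, in a risk paragraph, and not carried into the lists that staff would use.

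**On the analysis.** A reader might go further and say that early safety removals undermine the intention-to-treat comparison, because end-of-study testing is planned only for withdrawals after 6 months. The documents do not support that as a defect. Section VI already plans a mixed model under missing at random, multiple imputation and a completer sensitivity analysis, and no bias can be shown. Power barely moves if the losses stay within the planned 80 × 0.15 = 12. With a standardized difference of 0.69/0.93 = 0.742 and two-sided α of 0.05, a t-test has 85.4% power at 34 vs 34 and 84.9% at an assumed 30 vs 38. Imaging these subjects at month 12 would add 4 + 3.36 = 7.36 mSv, and a further 17.22/2 = 8.61 mSv for substudy participants. That is a trade-off for the investigators, not an error.

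**Conclusion.** Two points are wrong as written, at moderate severity.

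First, for K above 5.5 mEq/L confirmed on recheck in a subject on 50 mg twice daily, Sections VII and IX prescribe different actions, and nothing says which governs. The conflict covers every on-treatment potassium check after escalation, not the safety visits alone.

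Second, the metformin exclusion that Section VII relies on is not in the eligibility list or the on-study list, so those lists alone do not deliver the stated protection at either CTA.

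Neither point threatens the primary comparison. The number of subjects affected cannot be computed without a rate of confirmed hyperkalemia or of metformin use. The conclusion rests on the text alone and needs no assumption about either rate.

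**What to change.** **Potassium.** Put one rule in the Section VII Eplerenone paragraph, the Section IX text and the Section IX on-study list. Suggested rule: after a confirmed K >5.5 mEq/L, reduce from 50 mg twice daily to 50 mg daily and recheck; exclude if K is still >5.5 or if the subject was already on 50 mg daily; keep the existing exclusion for symptoms with K >5.0. The investigators and the DSMB may prefer immediate exclusion; what matters is that all three places agree.

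**Metformin.** Choose one of two routes:

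- Add metformin use to the Section III exclusions and metformin initiation to the Section IX list.
- Replace the Section VII sentence with an explicit rule for handling metformin around contrast at both CTAs.

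The sentence should not simply be deleted, since that would leave the risk unaddressed.

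**Cost.** One protocol amendment, text only. Excluding metformin users narrows eligibility by an amount that the documents do not give, and listing initiation as an on-study exclusion would remove subjects who start it. The handling rule avoids both.
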